6.8.4.6 SENSITIVITY ANALYSES

See “6.2.2 *Sensitivity analyses for register data based outcomes*”.

6.8.4.7 REPORTING AND STATISTICAL METHODS TO HANDLE MISSING DATA

See 6.8.1.7

6.8.5 AT 24 MONTHS: NUMBER OF RECURRENT SICK LEAVES AT 24-MONTH FOLLOW-UP (OUTCOME #15)

6.8.5.1 CALCULATION OF THE OUTCOME: SPECIFIC MEASUREMENT AND UNITS (AND TRANSFORMATION, WHERE APPLICABLE)

For each group, the number of persons who have experienced the event ‘stable return to work’ and followingly experienced the event ‘recurring sick leave’ is calculated. Recurring sick leave is defined as the first sick leave period starting with the first week of receiving sickness benefit after a period of stable return to work as defined in paragraph 6.8.1.1.

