1.2 SAP VERSION

This is the second version of the SAP.

¹ <https://clinicaltrials.gov/ct2/show/NCT02872051>

² <https://clinicaltrials.gov/ct2/show/NCT02885519>

Differences between version 1 and 2 are explicitly stated through a .docx-version of this newest version, where all changes are tracked, using the *Track changes* function in Microsoft Office Word. This file will be readily mailed through the corresponding author.

In brief, main changes revolves around the 24-month explorative outcomes: after analyses of 6- and 12-month outcomes we realized that results across work outcomes were heterogenous to a higher extent than expected. E.g., while the SAU group tended to have fastest RTW at 6-month follow-up, from explorative proportion over time-curves we realized that they might also tend to have a higher degree of recurrent sick-leave. Despite this, the SAU and INT groups still showed approx. the same number of weeks in work (when stability is disregarded) at 12-month follow-up. Followingly we speculate that the SAU group experiences faster RTW, but more recurrent sick leave. Therefore, we suggest that number of weeks in stable work is a better outcome, since this number is only high if RTW happens early, and if it is stable, and not disrupted by sick leave recurrence. We do though not know what stability threshold we should apply, and to *explore* this, we defined, prior to 24-month analyses, three different outcomes, with three different thresholds, see section 6.4. We plan these as sensitivity analyses.

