6.4 OUTCOME DEFINITIONS

The outcomes are reported as in the study design articles (except for selected outcomes, see alterations to SAP version 1 in appendix). The numbers 1 through 64 denotes the outcome numbers for reference purposes for this SAP section.

| PRIMARY AND SECONDARY OUTCOMES and outcome numbering | | | | | | |
|---|--------------------|--|--|--------------------------|---------------------------|---------------------------|
| Outcome class | Data source | Outcome | | 6-month follow-up | 12-month follow-up | 24-month follow-up |
| Primary | DREAM database | Time from baseline to RTW | | | 1 | |
| Secondary | DREAM database | Proportion in ordinary work | | | 2 | |
| | DREAM database | Time from baseline to RTW | | 3 | | 8 |
| | Questionnaire | Depressive symptoms measured by Beck Depression Inventory (BDI) ⁸ | | 4 | | |
| | Questionnaire | Anxiety symptoms measured by Beck Anxiety Inventory (BAI) ⁹ | | 5 | | |
| | Questionnaire | Stress symptoms measured by Cohen perceived stress scale (PSS) ¹⁰ | | 6 | | |
| | Questionnaire | Social and work related function measured by WSAS ¹¹ | | 7 | | |

| PREDEFINED EXPLORATORY OUTCOMES and outcome numbering | | | | | | |
|---|--------------------|--|---|-----------------|-----------------|----|
| Outcome class | Data source | Outcome | Follow-up | | | |
| | | | 6-month | 12-month | 24-month | |
| Pre-defined exploratory outcomes | DREAM database | Weeks in stable work (≥ 4 weeks) from baseline to current follow-up | | 9 | 10 | |
| | | Weeks in stable work (≥ 8 weeks) from baseline to current follow-up | | | 11 | |
| | | Weeks in stable work (≥ 12 weeks) from baseline to current follow-up | | | 12 | |
| | | Weeks in work from baseline to follow-up | | | 13 | |
| | | Proportion in ordinary work | | | 14 | |
| | | Number of recurrent sick leaves | | | 15 | |
| | Questionnaires | | Symptoms of Distress, anxiety, depression and somatization by Four-Dimensional Symptom Questionnaire (4DSQ) ¹² | 16 | 17 | 18 |
| | | | Depressive symptoms measured by Beck Depression Inventory (BDI) ⁹ | | 19 | 20 |
| | | | Anxiety symptoms measured by Beck Anxiety Inventory (BAI) ⁹ | | 21 | 22 |
| | | | Stress-symptoms measured by Cohen perceived stress scale (PSS) ¹⁰ | | 23 | 24 |
| | | | Social and work related function measured by WSAS ¹¹ | | 25 | 26 |
| | | | Burn-out symptoms measured by Karolinska Exhaustion Scale (KES) ¹³ | 27 | 28 | 29 |
| | | | Health-related quality of life measured by EQ-5D-5L ¹⁴ | 30 | 31 | 32 |

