6.6 OUTCOME BENEFIT DIRECTION

Referring to the hypothesis section, this table describes whether a “better outcome” is a higher or lower score on the numeric outcome variables.

| Outcome | Is “better outcome” defined by lower or higher numbers? | |
|---|---|----------------------|
| Time from baseline to RTW | Lower | |
| Proportion in stable work | | Higher |
| Time from baseline to RTW | Lower | |
| Weeks in work (all variations of stability definitions) | | Higher |
| Number of recurrent sick leaves | Lower ⁶ | |
| Depressive symptoms measured by Beck Depression Inventory (BDI) ⁸ | Lower | |
| Anxiety symptoms measured by Beck Anxiety Inventory (BAI) ⁹ | Lower | |
| Stress symptoms measured by Cohen perceived stress scale (PSS) ¹⁰ | Lower | |
| Social and work related function measured by WSAS ¹¹ | Lower | |
| Symptoms of Distress, anxiety, depression and somatization by Four-Dimensional Symptom Questionnaire (4DSQ) ¹² | Lower | |
| Burn-out symptoms measured by Karolinska Exhaustion Scale (KES) ¹³ | Lower | |
| Health-related quality of life measured by EQ-5D-5L ¹⁴ | | Higher ²¹ |
| General Quality of life scale measured by Flanagan's' QOLS ¹⁵ | | Higher |
| Self-efficacy concerning symptoms measured by IPQ subscale on personal control ¹⁶ | | Higher ²² |
| Return to work self-efficacy measured by RTW-SE ¹⁷ | | Higher |
| General self-efficacy measured by General Self-efficacy scale (GSS) ¹⁸ | | Higher |
| Client satisfaction with treatment measure measured by CSQ-8 ¹⁹ | | Higher |
| Presenteeism measured by Stanford Presenteeism Scale (SPS) ²⁰ | | Higher ²³ |

⁶ A low number of recurrent sick leave is a positive outcome only if duration of index sick leave is ideally balanced between compared groups.

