6.8.5.2 SPECIFIC ANALYSIS METHOD AND RESULT PRESENTATION

Only descriptive statistics will be performed for this outcome and no differences between groups will be tested. For each group, the number of persons who have experienced stable return to work and the number of persons who have experienced recurrent sick leave is presented.

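### Outcome #15 is labelled a number of sick leaves but counts persons with a first recurrence, and makes no allowance for time at risk after return to work

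*SAP*

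**What the plan says.** The outcome table in SAP section 6.4 lists exploratory outcome #15, at 24 months only, as "Number of recurrent sick leaves". The direction-of-benefit table in section 6.6 uses the same name and marks lower as better. Footnote 6 there adds: "A low number of recurrent sick leave is a positive outcome only if duration of index sick leave is ideally balanced between compared groups".

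Section 6.8.5.1 sets the quantity to be calculated: "For each group, the number of persons who have experienced the event ‘stable return to work’ and followingly experienced the event ‘recurring sick leave’ is" what is computed. It continues: "Recurring sick leave is defined as the first sick leave period starting with the first week of receiving sickness benefit", counted after a stable RTW as defined for the primary outcome (four consecutive weeks in work, dated to the first day of those weeks).

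On the analysis, section 6.8.5.2 states: "Only descriptive statistics will be performed for this outcome and no differences between groups will be tested". Per group it gives two counts: "the number of persons who have experienced stable return to work and the number of persons who have experienced recurrent sick leave is presented".

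Section 1.2 explains why the 24-month exploratory outcomes were revised. It reports that usual care (SAU) tended to return fastest at 6 months and that weeks in work at 12 months were about equal between SAU and the integrated arm. It then says: "Followingly we speculate that the SAU group experiences faster RTW, but more recurrent sick leave".

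**The concern.** There are two separate problems.

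First, the label and the definition describe different quantities. A number of sick leaves is a count of episodes. The definition gives a count of persons, each contributing at most one event, so second and later episodes are not captured.

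Second, follow-up for #15 runs from baseline to 24 months, but a person can have a recurrence only after a stable RTW. Time at risk is therefore 24 months minus the time to that return. If one arm returns sooner, more of its members enter the risk period and each stays in it longer. Neither count in section 6.8.5.2 records that exposure.

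At stake is how the 24-month results are read. Section 1.2 puts forward the idea that SAU returns faster but relapses more. Outcome #15 is the only listed outcome that measures recurrence directly. If SAU does return faster, #15 leans towards that reading even when recurrence after return is no more frequent in SAU.

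**Working it through.** **Inputs**

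- Window: 104 weeks from baseline (section 6.8.5, 24-month outcome).
- Stable RTW takes 4 weeks (section 6.8.1.1). A recurrence can therefore start from week 4 after the RTW date, and L = 104 − 4 = 100 weeks.
- Time to RTW in the slower arm: 210 days = 30 weeks (section 3.3), taken as the median of an exponential distribution.
- RTW hazard ratio (HR), faster against slower arm: assumed, 1.1 to 1.5. The upper value is the design effect in section 3.3. The SAP gives no size for the SAU tendency.
- Recurrence after return: assumed 30% per 52 weeks, constant hazard, the same in both arms. The SAP gives no figure.

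**The SAP's own figure.** The SAP states no number for #15. The only figure that uses the RTW inputs is the sample size, and it shows how the 210 days, which section 3.3 calls a mean, were used. Take two-sided α = 0.0167, power 0.9, 210 days as a median and 315 days in the other arm:

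- Events needed per group: 2(2.394 + 1.282)² / (ln 1.5)² = 27.02 / 0.1644 = 164.4.
- Averaged median (210 + 315)/2 = 262.5 days, so λ = ln 2 / 262.5 = 0.002641 per day.
- Event probability with A = 730 and F = 365: 1 − (e^(−365λ) − e^(−1095λ)) / (730λ) = 1 − (0.3814 − 0.0555)/1.928 = 0.831.
- n = 164.4 / 0.831 = 198 per group, as stated.

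So 210 days is read as a median below.

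**Formulas for #15.** Let a be the RTW hazard and h the recurrence hazard, per week.

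- Share with a completed stable RTW: S = 1 − e^(−aL)
- Share of the arm with a first recurrence: R = S − a(e^(−hL) − e^(−aL))/(a − h)
- Share among those who returned: R/S

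**Numbers.** h = −ln(0.7)/52 = 0.006859, so e^(−hL) = 0.5036.

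- Slower arm: a = ln 2/30 = 0.02310, S = 0.9008, R = 0.9008 − 0.02310 × (0.5036 − 0.0992)/0.01625 = 0.3256.
- Faster arm, HR 1.5: a = 0.03466, S = 0.9688, R = 0.9688 − 0.03466 × (0.5036 − 0.0313)/0.02780 = 0.3798.

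| RTW HR | Returned | Recurrence, % of arm | Excess (points) | Recurrence, % of returners | Excess (points) |
|---|---|---|---|---|---|
| 1.0 | 90.1% | 32.6 | – | 36.1 | – |
| 1.1 | 92.1% | 33.9 | 1.4 | 36.8 | 0.7 |
| 1.2 | 93.8% | 35.1 | 2.6 | 37.5 | 1.3 |
| 1.5 | 96.9% | 38.0 | 5.4 | 39.2 | 3.1 |

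The true recurrence hazard is the same in every row. Weeks at risk before a first recurrence, per person randomized, are R/h: 47.5 in the slower arm and 55.4 at HR 1.5. First recurrences per 100 weeks at risk are therefore 32.56/47.5 and 37.98/55.4, which is 0.69 in both.

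**Sensitivity at HR 1.5.** With recurrence of 20% or 40% per 52 weeks, the excess is 3.8 or 6.8 points of the arm, and 2.2 or 3.7 points among returners. With 210 days read as a mean and 198 per arm, 30% recurrence gives 74.4 against 82.7 persons. That is 37.5% against 41.8% of the arm, and 38.9% against 42.0% of returners. The direction is the same throughout.

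**The case against.** The strongest reply is that nothing is decided on #15. It is exploratory, descriptive and untested, and footnote 6 warns against the naive reading in advance. The answer section 1.2 gives to possible instability in SAU is weeks in stable work (#10 to #12), which combines speed and stability over the same 24 months and does not condition on having returned. Time to RTW at 24 months (#8) and weekly proportion-in-work curves to week 104 are also reported. All of this stands and limits the weight of the point. It does not remove it. The caveat supplies no measure that meets its own condition, and weeks in stable work cannot show whether recurrence itself differs.

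Four stronger readings are tempting, and the SAP does not support them:

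- A reader might infer that no denominator is given. Section 6.8.5.2 shows the number with stable RTW. Dividing by it cuts the artefact from 5.4 to 3.1 points at HR 1.5, but does not abolish it.
- A reader might take 5.4 points as the expected bias. HR 1.5 is the design effect for the intervention groups. Section 1.2 reports only a tendency for SAU at 6 months, and about equal weeks in work at 12 months.
- A reader might infer that section 1.2 declares footnote 6's condition unmet. It reports a tendency and calls its explanation speculation. It does not address the balance of index sick leave over 24 months.
- A reader might see recurrence, and so #15, as the basis of version 2. Section 1.2 describes heterogeneous work outcomes more broadly.

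It is also fair to say that a rate per person-week corrects exactly only under a constant hazard. With a declining hazard (Weibull shape 0.6, 30% at 52 weeks, HR 1.5), equal hazards give 0.64 against 0.62 first recurrences per 100 weeks, a small artefact in the other direction.

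**Conclusion.** The point holds and is minor. The mismatch between label and definition is plain from the text and needs no modelling. The dependence on time at risk follows from the fixed 24-month window, and its direction does not rest on the assumed values.

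Its size does. Under exponential RTW with a 30-week median in the slower arm and 30% recurrence per 52 weeks in both arms, an HR of 1.1 to 1.5 gives a spurious excess in the faster arm of 1.4 to 5.4 points of the whole arm. With the denominator the SAP presents, the excess is 0.7 to 3.1 points. If SAU's advantage in RTW speed is slight, the lower ends apply. No tested result and no sample-size figure is affected.

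**What to change.** In section 6.8.5, keep the outcome descriptive and make these changes:

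1. Report per arm the cumulative incidence of first recurrence counted from the date of stable RTW, censored at 24 months after baseline. This should lead, because it does not need a constant hazard.
2. As a supplement, report all recurrent episodes and the weeks at risk after first stable RTW, as episodes per 100 person-weeks.
3. Align the label in sections 6.4, 6.6 and 6.8.5 with what is counted: persons with a first recurrence, or episodes if those are reported.
4. State that these measures condition on having returned, which happens after randomization, so they are not randomized comparisons between arms.

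The cost is a few lines of SAP text and a little extra descriptive analysis. The weekly register data already used for the work outcomes supply the dates, so no new data are needed.

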6.8.5.2 SPECIFIC ANALYSIS METHOD AND RESULT PRESENTATION

Only descriptive statistics will be performed for this outcome and no differences between groups will be tested. For each group, the number of persons who have experienced stable return to work and the number of persons who have experienced recurrent sick leave is presented.

6.8.6 HARM MEASURES AT 12-, AND 24-MONTH FOLLOW-UP (OUTCOME #49-64)

6.8.6.1 CALCULATION OF THE OUTCOME: SPECIFIC MEASUREMENT AND UNITS (AND TRANSFORMATION, WHERE APPLICABLE)

For each group, the number of persons who have experienced the harmful event is calculated.

6.8.6.2 SPECIFIC ANALYSIS METHOD AND RESULT PRESENTATION

Only descriptive statistics will be performed for this outcome and no differences between groups will be tested.

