4 STATISTICAL PRINCIPLES

4.1 CONFIDENCE INTERVALS AND P-VALUES

For all outcomes, the three randomization groups are pairwise compared. Due to these multiple comparisons, we will calculate 98,3% confidence intervals, according to Bonferroni correction of desired α -level of 0,05 in testing of 3 hypotheses:

$$\alpha\text{-level: } 0,05 \times \frac{1}{3} \cong 0,0167 \Rightarrow \text{Confidence Interval: } 1 - 0,0167 \cong 98,33\%$$

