6 ANALYSIS

The first subsections of this section 6, describes general strategies applying to all analyses unless otherwise specifically stated. Subsection 6.8 contains the separate analysis strategies per outcome in 6.8.x.

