6.5 HYPOTHESES AND NULL-HYPOTHESES

Stated below are the generic versions of all three hypotheses (H_1) and all three null-hypotheses (H_0) that apply to each outcome.

Regarding what is a “better outcome” is listed in section 6.6, defined for each outcome measure, respectively.

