6.5.1 HYPOTHESES

This superiority trial hypothesizes that, for all outcomes,

H_{1A} Group 3, “Integrated IBBIS mental health care treatment and vocational rehabilitation”
conveys better outcomes than
Group 2, “IBBIS mental health care (and standard VR)”, and

H_{1B} Group 2, “IBBIS mental health care (and standard VR)”, and
conveys better outcomes than
Group 1, “Control group, treatment as usual (standard MHC and standard VR)”
and followingly

H_{1C} Group 3, “Integrated IBBIS mental health care treatment and vocational rehabilitation”
conveys better outcomes than
Group 1, “Control group, treatment as usual (standard MHC and standard VR)”
and followingly

Group 3 conveys better outcomes than Group 1,

since if

Group 3 outcome > Group 2 outcome > Group 1 outcome

then

Group 3 outcome > Group 1 outcome.

The groups are thoroughly described in the IBBIS Protocol and the SDAs.

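### Harm measures are reported as counts per arm, with no between-arm estimate, interval or stated denominator, although section 4.1 promises pairwise 98.3% intervals for all outcomes

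*SAP*

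**What the plan says.** The general rule in SAP section 4.1 is: "For all outcomes, the three randomization groups are pairwise compared. Due to these multiple comparisons, we will calculate 98,3% confidence intervals". It names no exception. The outcome tables in 6.4 number the harm measures among the outcomes (49 to 58 and 61 to 64, fourteen entries), so on its wording the rule covers them.

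For the harm measures, 6.8.6.1 defines the quantity: "For each group, the number of persons who have experienced the harmful event is calculated". Section 6.8.6.2 then fixes the presentation: "Only descriptive statistics will be performed for this outcome and no differences between groups will be tested". No risk, difference, ratio, interval or denominator is named.

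Other sections that bear on the point:

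- Section 4.2 makes analyses intention-to-treat by default.
- Section 5.1 deletes the data of participants who withdraw consent but keeps their study ID and allocation.
- Section 6.7 promises the proportion of missing data per group for all outcomes.
- Section 6.7.1 deals only with the DREAM outcomes, whereas the 6.4 table attributes harms to LPR.
- Section 6.2.2 defines best and worst cases for withdrawn participants only in terms of returning to work.

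**The concern.** The rule in 4.1 and the method in 6.8.6 do not agree. More important is what the reader of the harm table will be given. A count per arm does not state how much excess risk remains compatible with the data, and the trial was sized for return to work, not for harms. For rare events (suicide, death) equal or zero counts say very little. For commoner events (admissions, emergency contacts) the data may carry real information about a difference, and the plan asks for neither its size nor its precision.

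The denominator adds to this. Withdrawn participants remain in the randomized total, but their events cannot be known. Section 6.8.6 does not say whether a count is to be read against all randomized or against those with register data to that follow-up. Sections 6.8.1 to 6.8.4 each have a missing-data subsection; 6.8.6 has none.

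**Working it through.** **Inputs from the SAP.** Section 4.1: α = 0.05/3 = 0.0167 per comparison, interval level 98.33%. Section 3.3: 198 per group (power 0.9) or 153 (power 0.8). The SAP gives no event rate, margin or power for any harm, so the event risks and counts below are assumptions. α is taken as two-sided, since sidedness is not stated.

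**The plan's own figures.** 0.05/3 = 0.016667 and 1 − 0.016667 = 98.33%, as stated. The group sizes follow from n = (z₁₋α/₂ + z_power)² / (ln 1.5)² × (1/p_A + 1/p_B), with exponential times, 730 days of accrual and 365 days of follow-up. Medians of 210 and 315 days give p_A = 0.8868 and p_B = 0.7771, hence n = 198.4 and 153.8. An average-median variant gives 197.8 and 153.3. Both agree with the stated 198 and 153 to within rounding.

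**Zero events in one arm.** Exact two-sided upper limit = 1 − (α/2)^(1/n).

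| n per arm | 98.3% (α/2 = 1/120) | 95% (α/2 = 1/40) |
|---|---|---|
| 198 | 2.4% | 1.8% |
| 153 | 3.1% | 2.4% |

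**A doubling of a commoner harm, assumed 5% vs 10%, 198 per arm.** Expected counts are 0.05 × 198 ≈ 10 and 0.10 × 198 ≈ 20. SE = √[(0.05 × 0.95 + 0.10 × 0.90)/198] = 0.0264. The half-width is 2.394 × 0.0264 = 6.3 points at 98.3% and 1.960 × 0.0264 = 5.2 points at 95%. The 98.3% interval is therefore about −1.3 to +11.3 points.

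**Equal counts, 198 per arm, 98.3% level** (Newcombe score-based interval for the risk difference, log-scale interval for the risk ratio):

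| Assumed counts | Risk difference | Risk ratio |
|---|---|---|
| 0 vs 0 | ±2.8 points | not estimable |
| 2 vs 2 | ±3.6 points | 1.0 (0.09 to 10.8) |
| 10 vs 10 | ±5.8 points | 1.0 (0.35 to 2.8) |
| 20 vs 20 | ±7.5 points | 1.0 (0.49 to 2.05) |

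At 153 per arm, 0 vs 0 gives ±3.6 points and 10 vs 10 gives ±7.4 points.

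**Power to detect a doubling at α = 0.0167.** From assumed control risks of 1%, 2%, 5% and 10%, power is 5.7%, 10.9%, 30.6% and 65.4% at 198 per arm, and 4.7%, 8.5%, 23.1% and 52.2% at 153. Testing would therefore achieve little for rare harms, which supports leaving them untested. It also means that similar counts would be weak evidence of similar risk.

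**The case against.** **The plan is explicit.** Section 6.8.6.2 leaves no doubt about what will be done for harms, and outcome 15 is handled the same way, with counts only ("For each group, the number of persons who have experienced stable return to work and the number of persons who have experienced recurrent sick leave"). This stands: a reader might infer that the plan is ambiguous, and it is not. The defect in 4.1 is a missing exception.

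**Section 6.5 does not truly conflict.** Its wording is sweeping ("This superiority trial hypothesizes that, for all outcomes"), but the introduction to section 6 says that its opening subsections give "describes general strategies applying to all analyses unless otherwise specifically stated", and 6.8.6.2 is such a statement. The direction table in 6.6 also lists no harm measure, so superiority on harms is not even defined. This largely stands for 6.5. It does not rescue 4.1, which lies outside section 6.

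**Missing data are covered.** Section 6.7 reports missingness per group for all outcomes and 5.2 reports group sizes. A reader might infer that withdrawn participants will be passed off as event-free; with 6.7 in force the SAP does not support that. What remains is that N for the harm counts is not fixed.

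**Counts and group sizes let anyone compute the interval.** True for an unadjusted binary outcome once N is known, and descriptive statistics need not exclude percentages. What is missing is the display, not the information.

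**The levels are a choice.** Section 4.1 sets 98.3% for pairwise comparisons, not for a single-arm limit, and a zero count has only an upper limit. A one-sided 95% limit, 1 − 0.05^(1/n), is 1.5% at 198 and 1.9% at 153. This is fair, and the message does not change.

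**More intervals invite informal testing.** This is a real cost, taken up under the fix.

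**Conclusion.** The point holds as a reporting weakness with an unreconciled general rule. Section 4.1 promises pairwise 98.3% intervals without exception; 6.8.6 provides counts only, with no between-arm estimate, interval or defined N. At the planned sizes, zero events leaves a risk of up to 2.4% open at 198 per arm (3.1% at 153; 1.8% and 2.4% at the 95% level). An assumed doubling from 5% to 10% would be estimated only to within about 6.3 points either way. Intervals would display this imprecision; they would not remove it.

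A reader might go further and infer that the trial will declare its interventions harmless from similar or zero counts, or that harms ought to be tested. The SAP supports neither: it states no such conclusion, and declining to test rare harms is sound. The figures rest on the planned arm sizes and, apart from the zero-event limits, on assumed event risks or counts.

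**What to change.** Replace 6.8.6.2 with text to this effect:

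> For each harm measure we report n/N (%) per arm, where N is the number of participants with register coverage to that follow-up, and the number without coverage. We give the three pairwise risk differences with score-based or exact 98.3% confidence intervals and, where an arm has no events, the exact upper limit for that arm. These are descriptive. No significance test is made and no significance is claimed.

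In 4.1 and 6.5, state that harm measures are estimated and not tested for superiority. The exception in 4.1 should also name outcome 15, which is descriptive only.

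The cost is SAP wording and a short addition to the tables. Fourteen harm outcomes by three pairs gives 42 intervals per trial (84 over both), at a level corrected for three comparisons and not across harms. Some readers will treat an interval that excludes zero as a test, so the label must be prominent. Section 1.2 says that 6- and 12-month outcomes had been analysed before this version, and 3.5 says that the 24-month analyses are unblinded. Any interval added after results were seen should therefore be marked as a later addition.
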